5.3 Receipt

At the Month 6 visit, a 3-month supply of drug will be prescribed by study investigator and obtained through insurance and filled at pharmacy of choice. Subjects will be prescribed another 3-month supply at Month 9 visit. Subjects will take this medication as instructed and return to the clinic at Month 9 and Month 12 for routine care visits, inclusive of dosing compliance assessment.

5.4 Storage

UDCA will be stored at 20C to 25C (68F to 77F) and dispensed in a tight container.

5.5 Preparation and Packaging

Each URSO 250® elliptical, biconvex, film-coated tablet, white, engraved with "URS785", contains 250 mg of UDCA. Available in bottles of 100 tablets (NDC 58914-785-10) and 500 tablets (NDC 58914-785-50). Each URSO Forte® elliptical, biconvex, scored, film-coated tablet, white, engraved with "URS790", contains 500 mg of ursodiol. Available in bottles of 100 tablets (NDC 58914-790-10) and 500 tablets (NDC 58914-790-50).

Actigall Capsules are opaque white and pink capsules imprinted "ACTIGALL" on one half and "300 mg" on the other half of the capsule in black. Bottles of 100 are supplied with child-resistant closures. (NDC 0023-6145-01)

5.6 Administration, Accountability, and Subject Dosing Compliance Monitoring

The investigator or his/her designated and qualified representatives will prescribe study drug only to subjects enrolled in the study in accordance with the protocol. The study drug must not be used for reasons other than that described in the protocol. At the start of the study, each subject should receive counseling regarding the importance of dosing compliance. At visits following the initiation of dosing, study site personnel will assess subject compliance by asking subjects if any doses were missed. Treatment compliance will be based on the subjects' responses, as recorded in source.

6 Study Procedures

Schedule of study assessments

Activity	Screening (CV)	Month 0 (PC)	Month 3 (CV/PC)	Month 6 (CV)	Month 9 (CV/PC)	Month 12 (CV)	Month 18 follow-up (CV)	Month 24 follow-up (CV)
Informed consent	X*					X*		

Demographics & medical history (including assessment of liver disease)	X							
Urine pregnancy test for WOCBP	X*			X*	X*	X*		
Physical exam & vital signs	X		X	X	X	X	X	X
Fibroscan	X			X*		X	X*	X
¹³ C-methacetin breath test (optional sub-study)***				X*		X*		
QoL questionnaire	X*			X*		X*	X*	X*
Concomitant medication assessment	X	X*	X	X	X	X	X	X
Adverse event assessment		X*	X*	X*	X*	X*	X*	X*
Drug initiation				X*				
Weight-based daily dosage calculation (if in-person visit)					X	X	X	X
Drug accountability & adherence assessment					X*	X*	X*	X*
Blood draw: clinical laboratory assessments:** -LFP -CBC -GGT	X		X	X	X	X	X	X
Blood draw: research lab assessments: -ACE -sIL2R -optional research samples	X*			X*		X*	X*	X*

*Research specific activity

**Subjects can have labs drawn at the laboratory of their choice

CV = clinic visit; PC = phone call; QoL = Quality of Life

LFP = liver function panel; CBC = complete blood count; GGT = gamma-glutamyl transferase

*** **NOTE: All subjects enrolled under Amendment 10 (JUN 2021) or later will NOT be included in the optional MBT sub-study.**

6.1 Screening

The following procedures are completed during the screening visit:

- Informed Consent
- Record medical history, which includes questions about social history, smoking, alcohol use, and disease history
- Record prior and current medications
- Record general health (including averse events and illnesses)
- A physical examination, including assessment of certain physical symptoms that are associated with liver disease
- Quality of Life questionnaire
- Vital signs, which include blood pressure, heart rate, breathing rate, body temperature, will be measured. height and weight may also be recorded
- A Fibroscan (ultrasound scan of abdomen to measure the stiffness of liver). *Fibroscan results available within a month of screening may be used in place of a repeat at screening*

- Blood samples will be collected for routine & research laboratory tests (about 3 tablespoons, 30 mL) and to test for liver function
- Urine pregnancy test for women of child-bearing potential

6.2 Study Observational Phase

Assessments during the observational phase will include the following procedures:

- Review prior and current medications
 - Record general health (including adverse events and illnesses)
 - A physical examination, including assessment of certain physical symptoms that are associated with liver disease*
 - Vital signs, which include blood pressure, heart rate, breathing rate, body temperature, will be measured. height and weight may also be recorded*
 - Blood samples will be collected for routine laboratory tests (about 2 tablespoons, 20 mL) and to test for liver function
- *if in-person clinic visit is conducted

6.3 Study Intervention Phase

Clinic visits during the interventional phase will include the following procedures:

- Review prior and current medications
- Record general health (including adverse events and illnesses)
- A physical examination, including assessment of certain physical symptoms that are associated with liver disease
- Quality of Life questionnaire
- Vital signs, which include blood pressure, heart rate, breathing rate, body temperature, will be measured. height and weight may also be recorded
- A Fibroscan (ultrasound scan of abdomen to measure the stiffness of liver)
- Blood samples will be collected for routine & research laboratory tests (about 3 tablespoons, 30 mL) and to test for liver function
- MBT performed (month 6 and month 12) if subject has consented to optional sub-study
- Study drug instruction (month 6)
- Study drug compliance assessment
- Weight-based daily dosage calculation
- Urine pregnancy test for women of child-bearing potential

6.4 End of Study/Early Termination Visit

If subjects complete the interventional phase of the study, or decide to end participation, an End of Study visit will include the following:

- Review prior and current medications
- Record general health (including adverse events and illnesses)
- A physical examination, including assessment of certain physical symptoms that are associated with liver disease
- Quality of Life questionnaire
- Vital signs, which include blood pressure, heart rate, breathing rate, body temperature, will be measured. height and weight may also be recorded
- A Fibroscan (ultrasound scan of abdomen to measure the stiffness of liver)
- MBT performed if subject has consented to optional sub-study
- Blood samples will be collected for routine laboratory tests (about 2 tablespoons, 20 mL) and to test for liver function

- Study drug compliance assessment

6.5 Follow Up Phase (Optional)

Subjects will have the option to remain on UDCA after study completion if it can be obtained through prescription outside of the trial. Subjects will be seen at 2 additional clinic visits which will consist of the following:

- Review prior and current medications
- Record general health (including adverse events and illnesses)
- A physical examination, including assessment of certain physical symptoms that are associated with liver disease
- Quality of Life questionnaire
- Vital signs, which include blood pressure, heart rate, breathing rate, body temperature, will be measured. height and weight may also be recorded
- A Fibroscan (ultrasound scan of abdomen to measure the stiffness of liver)
- Blood samples will be collected for routine laboratory tests (about 2 tablespoons, 20 mL) and to test for liver function
- Study drug compliance assessment (when applicable)
- Weight-based daily dosage calculation

6.6 Unscheduled Visits

Unscheduled/safety visits may be conducted at any time and may repeat assessments. This is not common but may be necessary to ensure subjects overall health and safety. Similarly, in case of any important findings from study laboratory tests, physical exams or any side effects that may be related to the study drug, PI may follow up for as long as necessary/until the condition or side effect stabilizes, resolves, or is no longer of concern. Follow-up may include any additional assessments needed to understand the nature or cause of the event and may include collection of additional blood samples, other assessments, or consultation with other healthcare professionals.

6.7 Subject Withdrawal

Subjects may withdraw from the study at any time without impact to their care. They may also be discontinued from the study at the discretion of the PI for lack of adherence to intervention or study procedures or visit schedules, AEs, or upon the development of varices, ascites or encephalopathy, doubling of serum bilirubin, marked worsening of fatigue or pruritus, inability to tolerate the drug, or voluntary withdrawal. . The PI may also withdraw subjects who violate the study plan, or to protect the subject for reasons of safety or for administrative reasons. It will be documented whether or not each subject completes the clinical study. Subjects who withdraw early will be asked to have one final visit to collect investigational product and to follow up regarding adverse events.

Requirements for stopping the study:

The study will be stopped if there is a pattern seen of adverse events related to the MBT test among the subjects. Since this is a small pilot study if serious adverse events related to the MBT test are seen in one subject the study will be stopped.

Stopping Criteria for Administration of MBT Test:

- Prior occurrence of any adverse events related to 13C-Methacetin solution and device
- Change in subject's health which makes continued participation unsafe. PI will see subject prior to administration of test.
- Subject has not followed the pre-requisites for taking the MBT test (e.g., requirements for fasting, caffeine consumption, general anesthesia, use of excluded medications).

Early Termination of the Breath Test:

Key personnel will be trained how to terminate the breath test early if a subject is unable to complete the full 75 minutes of breath collection. In the following situations, the breath test collection will be terminated:

- The subject vomits.
- The subject has to be disconnected from the nasal cannula/ collection device for more than 1 minute due to an urgent procedure.
- The subject is inadvertently disconnected from the BreathID® MCS device.
- The BreathID® MCS device malfunctions.

Should an interruption in breath collection due to removal of the cannula or its disconnection occur during the administration of the MBT and the device cannot compute the delta over baseline results, the test may be repeated at a different date (minimum time allowed before repeating is 24 hours) provided the subject still qualifies and is willing to repeat testing. If the interruption occurred at the beginning of the Breath Test (during baseline breath collection) and before ingestion of the 13C-Methacetin solution, the test can be repeated immediately.

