6.7.1 Data Collection and Follow-up for Withdrawn Subjects

If subjects withdraw from the study, the information that was collected before withdrawal will still be used. No new information will be collected without subject permission except to follow up on safety events that might have happened during the study.

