6.8 Clinical Laboratory Tests

Category	Tests
Hematology	RBC, hemoglobin, hematocrit, platelet count, WBC with differential
Liver associated tests (Hepatic function panel)	SGOT/AST, SGPT/ALT, total Bilirubin, GGT, ALP, Albumin

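### PI discontinuation for worsening ends study participation, and the plan does not clearly secure outcome data from those subjects, so the UDCA effect may be overstated by an unknown amount

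*Combined protocol and SAP*

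**What the plan says.** Section 6.7 (Subject Withdrawal) says of subjects: "They may also be discontinued from the study at the discretion of the PI". The listed reasons include varices, ascites and encephalopathy, and also "doubling of serum bilirubin, marked worsening of fatigue or pruritus, inability to tolerate the drug". They also include poor adherence and administrative grounds. On the last contact it says: "Subjects who withdraw early will be asked to have one final visit to collect investigational product and to follow up regarding adverse events".

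Section 6.4 (End of Study/Early Termination Visit) describes a different last contact: "If subjects complete the interventional phase of the study, or decide to end participation, an End of Study visit will include the following". Its list has the "Quality of Life questionnaire", a Fibroscan, and this: "Blood samples will be collected for routine laboratory tests (about 2 tablespoons, 20 mL) and to test for liver function". Section 6.8 defines the liver panel as "SGOT/AST, SGPT/ALT, total Bilirubin, GGT, ALP, Albumin", so ALP and GGT would be measured there.

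Section 6.7.1 keeps everything gathered before withdrawal. After that: "No new information will be collected without subject permission except to follow up on safety events".

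The schedule in section 6 has no early-termination column. It places the questionnaire and Fibroscan at Months 6 and 12 but not at Month 9; liver bloods are drawn at Months 6, 9 and 12. UDCA starts at the Month 6 visit. Section 7.5 defines an all-treated population. Sections 7.1 to 7.4 name no analysis timepoint and do not say how an early-termination or missing value is used.

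**The concern.** Discontinuation under 6.7 is from the study, so a subject who worsens on UDCA can stop contributing outcome data at the moment when the data are least favourable to the drug. Several of the reasons are close to what the trial measures. Bilirubin belongs to the liver panel, and two PROMIS Fatigue forms are among the attached questionnaires (section 15). Section 1.2.1 shows that a US trial in PBC counted much the same events as treatment failures in its main efficacy endpoint. Here nothing says how such subjects are counted.

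All subjects receive UDCA after an observational period, and there is no concurrent untreated group in which a similar loss would offset this one. Sections 7.3 and 7.4 say that the effect size from this pilot will be used to power a multicentre trial. An inflated estimate would make that trial too small.

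**Working it through.** The plan states no dropout rate, SD, effect size or power, so there is no figure of its own to reproduce. The check has two parts.

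**1. Which outcome data does an early leaver have?**

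- *Subject who chooses to leave.* Section 6.4 applies on its own words, so ALP/GGT, Fibroscan and questionnaire are due. Section 6.7 mentions only product return and adverse events. The two sections need reconciling.
- *Subject discontinued by the PI.* The trigger in 6.4 is completion or the subject's own decision, so coverage is unclear. The schedule does not settle it.
- *Subject who leaves between Months 6 and 9.* By the schedule there is no on-drug ALP/GGT, Fibroscan or PROMIS value unless the 6.4 visit is held.
- *Subject who leaves between Months 9 and 12.* A Month 9 ALP/GGT exists if it was drawn. By the schedule there is still no on-drug PROMIS or Fibroscan. (The general list in 6.3 includes both without saying at which visits.)

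A value from an early 6.4 visit is also not a Month 12 value. ALP/GGT is therefore better protected than PROMIS or Fibroscan, and neither enzyme is among the reasons in 6.7.

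**2. How large could the selection effect be?** This is an illustration under assumptions. Let a fraction *d* of treated subjects, the worst on a normally distributed worsening score, leave unmeasured. Let that score have correlation *ρ* with the endpoint change, and let the true mean change be zero. The completers' mean then shifts towards benefit by

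shift = ρ × φ(z₁₋d) / (1 − d), in SDs of the change.

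For *d* = 10%: φ(1.282) / 0.90 = 0.1755 / 0.90 = 0.195. For *d* = 20%: φ(0.842) / 0.80 = 0.2800 / 0.80 = 0.350.

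| ρ (assumed) | d = 10% | d = 20% |
|---|---|---|
| 1 | 0.195 | 0.350 |
| 0.6 | 0.117 | 0.210 |
| 0.3 | 0.058 | 0.105 |
| 0 | 0 | 0 |

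Simulation at ρ = 0.6 agrees: 0.10 and 0.19 with 10 subjects, and 0.11 and 0.20 with 40.

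If half of the leavers are measured at a 6.4 visit and included, the shift is (d/2) × m / (1 − d/2), where m = ρφ/d is the leavers' mean. At ρ = 0.6:

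- d = 10%: m = 0.6 × 0.1755 / 0.10 = 1.053, and 0.05 × 1.053 / 0.95 = 0.055.
- d = 20%: m = 0.6 × 0.2800 / 0.20 = 0.840, and 0.10 × 0.840 / 0.90 = 0.093.

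If all leavers are measured and included, the shift is zero.

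**The case against.** A reader might infer from 6.7 alone that early leavers have no ALP/GGT or quality-of-life data at all. The documents do not support that. Section 6.4 has early termination in its title and lists both. Its trigger and the wording of 6.7 can be read as describing the same people, and 6.7 may state only the purpose of the last visit without excluding the 6.4 procedures.

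Other points on that side also stand:

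- No completers-only analysis at Month 12 is specified. The population is all-treated, and data from before withdrawal are kept.
- The PI may discontinue but need not, and some listed reasons, such as poor adherence, may be unrelated to the endpoint. The model, which removes exactly the worst subjects, is therefore an extreme case.
- The fatigue reason is a clinical judgement with no PROMIS threshold, so even for fatigue a correlation of 1 is an upper limit. There is no pruritus endpoint.
- The 20% fall in ALP and GGT in section 1.3 governs dose adjustment at Month 9. It is not an efficacy benchmark against which to judge the bias.
- With 10 subjects the standard error of a mean change is 1/√10 = 0.32 SD, larger than most of the shifts above. With 40 it is 1/√40 = 0.16 SD. The bias, however, does not shrink as enrolment grows.
- Section 6.7.1 respects consent and is not a defect.

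What survives is that 6.4 does not clearly reach subjects discontinued by the PI, that the two sections describe different last visits, and that no rule says what value an early leaver contributes.

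**Conclusion.** The point holds as a possible bias of unknown size, and it is cheap to reduce. Followed as written, 6.7 can lose post-dose data from subjects who worsen, most of all PROMIS and Fibroscan, which the schedule places on drug only at Month 12. ALP/GGT is less exposed.

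A reader might go further and conclude that the UDCA benefit is overstated. That would need three things together: leavers who are unmeasured, an analysis restricted to completers, and leaving that is correlated with the endpoint. The documents establish none of them. The range of 0 to 0.35 SD for a loss of 10% to 20% shows only what would follow from assumed fractions and correlations. The direction, where there is a bias of this kind, favours UDCA.

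**What to change.** 1. Reconcile 6.4 and 6.7 so that every early leaver, including those discontinued by the PI, is asked for the 6.4 assessments. Add an early-termination column to the schedule.
2. In 6.7, separate stopping UDCA from leaving the study. Ask subjects who stop UDCA to keep the Month 9 ALP/GGT and the Month 12 ALP/GGT, Fibroscan and PROMIS assessments unless they withdraw consent. This fits 6.7.1.
3. In section 7, say that all treated subjects are summarised with these values whether on or off drug, how early-termination and missing Month 12 values are handled, and that discontinuations are reported by reason.

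None of this changes who stops treatment or why. The cost is protocol wording, a few off-drug values that may make the estimate slightly less favourable, and some extra assessments. Section 12.3 bills Fibroscan and laboratory tests to subjects or their insurance, so payment for any additional ones should be settled. The schedule marks the questionnaire as research-specific.

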6.7.1 Data Collection and Follow-up for Withdrawn Subjects

If subjects withdraw from the study, the information that was collected before withdrawal will still be used. No new information will be collected without subject permission except to follow up on safety events that might have happened during the study.

6.8 Clinical Laboratory Tests

Category	Tests
Hematology	RBC, hemoglobin, hematocrit, platelet count, WBC with differential
Liver associated tests (Hepatic function panel)	SGOT/AST, SGPT/ALT, total Bilirubin, GGT, ALP, Albumin

6.9 Optional Research Blood Sample Collection

Subjects who provide informed consent for the collection and use of their blood samples for future research will have samples collected every 6 months during the course of their study participation. All samples will be de-identified prior to being stored. Subjects who do not consent to this optional collection will still be able to participate in the rest of the study.

6.10 Efficacy Evaluations

Standard of care laboratory tests for liver function: See 3.2.1, 6.7

FibroScan® as a standard of care measure for liver stiffness (3.2.2):

Transient elastography is a non-invasive, reproducible method for measuring liver stiffness that correlates with liver fibrosis and will be measured using FibroScan® (manufacturer Echosens). An ultrasound transducer probe is mounted on the axis of a vibrator; vibrations of mild amplitude and low frequency are transmitted by the transducer, inducing a wave that propagates through the underlying tissue. The propagation velocity of the wave is then measured. The velocity is directly related to tissue stiffness; the stiffer the tissue, the faster the wave propagates

Methacetin Breath Test for liver metabolic capacity (3.2.2, optional, exploratory):

The ¹³C-methacetin breath test (MBT) is a noninvasive tool to assess liver microsomal capacity to metabolize the nonradioactive ¹³C-labeled Methacetin. The Breath Test System consists of the BreathID® Molecular Correlation Spectrometry (MCSTM) device and a test kit containing a

breath collection nasal cannula and a nonradioactive isotope ^{13}C -methacetin solution. The BreathID MCS device measures and computes the $^{13}\text{CO}_2/^{12}\text{CO}_2$ ratio in the subject's exhaled breath in real time. Additional details for the procedure are provided in Appendix 5 (16.5).

Subjects will be asked to sit in a chair with a nasal cannula (a small tube) attached to the BreathID MCS device placed inside their nostrils while breathing normally. The BreathID MCS device will measure the subject's baseline carbon dioxide production for approximately 10 minutes (up to 25 minutes), after which the subject will be administered 1 cup of a solution of a 75 mg Methacetin pre-dissolved in water. Methacetin is exclusively broken up in the liver and turns into carbon dioxide and acetaminophen. The subject will remain sitting in a chair with the nasal cannula in their nose breathing in a normal fashion for another 60 minutes while the BreathID MCS device measures carbon dioxide production. The MBT will be performed at screening, Month 6, and Month 12 for this protocol.

6.11 Safety Evaluations

Laboratory tests for liver function and adverse event reporting: See 3.2.2.

7 Statistical Plan

7.1 Primary Endpoint

The primary end-point is a reduction in ALP and/or GGT from baseline.

7.2 Secondary Endpoints

To assess the safety and tolerability of UDCA in patients with hepatic sarcoidosis, liver function tests will be monitored alongside reporting of adverse events.

To assess efficacy of UDCA in the improvement of liver stiffness as a clinical parameter of liver function, Fibroscan stiffness readings (in kPa) will be monitored.

To assess quality of life parameters prior to and following intervention with UDCA, PRO questionnaire scores will be assessed for improvements.

To assess changes in metabolic capacity of the liver, ^{13}C -methacetin breath tests will be analyzed and resulted in all subjects prior to and following intervention with UDCA (exploratory endpoint).

